4. TARGET STUDY POPLUATION SPECIFICS

Recruitment procedures: We will use our electronic tracking system to identify potential participants who will be approached sequentially based on arrival and availability (e.g., we will not interrupt patient care). Patients may be approached in private areas of waiting rooms or treatment spaces. Interested patients will initially complete a screening survey. For subjects reporting no previous sexual activity, their involvement in the study will terminate upon screening survey completion.

For eligible youth who agree to participate during the iterative revision process, all youth will receive the intervention until six adolescents have been enrolled. After that time, all eligible and interested participants will be randomized to treatment or control arm.

Based on prior work demonstrating differences in STI and pregnancy testing due to presence of genito-urinary symptoms, we will ensure balanced allocation of participants reporting genitourinary complaints (i.e., concern for pregnancy/sexually transmitted infection, lower abdominal pain, urinary complaints, genital pain or discharge, or vomiting in a female patient) between treatment groups in a 1:1 ratio. We will generate our randomization sequence using REDCap, which will also host our computerized surveys. We will recruit participants during times when adolescents are more likely to visit the ED, using ED arrival data from the previous year to determine recruitment times and we will weight recruitment shifts based on the proportion of adolescents who presented during each block for weekdays (Monday-Thursday)

and weekends (Friday-Saturday). After survey completion, participants will be randomized to receive the intervention or control arm. Randomization will be assigned based on computer-generated algorithm and using numbered sealed envelopes.

Inclusion/Exclusion Criteria

Inclusion: Part 1 (BASELINE) Adolescents who present for care to the CMH Main ED for any reason who 1) are aged 14-19 years and 2) reside within 30 minutes travel time of CMH will be eligible to complete the computerized health behavior screening survey. We selected thirty minute travel time (per subject self-report) to facilitate potential clinic referral.

Part 2 (INTERVENTION) and (Part 3 Post-Intervention survey for Formative Group)

Adolescents who report previous sexual activity on screening survey will be eligible to participate as part of the formative group or within the randomized trial. For subjects reporting no previous sexual activity on the screening survey, their involvement in the study will terminate upon survey completion.

Exclusion: Subjects who are unable to provide consent (i.e., determined to be too ill by the ED team, have cognitive impairment due to chronic condition or acute medical concern), are in police custody, are seeking care due to sexual assault or psychiatric emergency, or do not speak English will be excluded. We will also exclude patients if they are under the clinical care of a study investigator working in the ED (i.e., [name] or [name]).

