We will collect immediate post-intervention survey data from all participants. The health educator will complete a survey following each intervention. We will collect data on health services (i.e., STI/pregnancy testing, condoms, emergency contraception, hormonal contraception, STI treatment, HIV testing, referral to clinic) offered, accepted, and completed as well as services provided as part of ED clinical care. When determining completion of sexual health services, services that are completed via a standing order or protocol (e.g., adolescent female receiving urine pregnancy test before radiographic imaging) will be noted and not included when determining our outcome measurement.

Incentives

Compensation for the formative group will be up to \$55.00.

Part 1 Take survey	Part 2 Meet with the Health Educator	Part 3 Take survey about meeting with the Health Educator
\$5.00	\$30.00	\$20.00

Compensation for the RCT will be up to \$80:

\$5 for completing the screening survey, if the subject does not qualify or decides not to continue in the study, their participation will be over and they will receive a \$5.00 Target® gift card.

If a subject qualifies to continue in the study and signs the written consent they will receive a Greenphire Clincard instead of the Target® card. If they continue in the study they will be randomized into study group. At the end of this visit they will receive the Greenphire Clincard gift card. It will be uploaded with \$5.00 for taking the computerized survey and \$30 for completing the randomization part of the visit for a total of \$35.00. An additional \$10-each will be loaded onto the Greenphire Clincard when month 2 and month 4 surveys are completed and final \$25 for month 6 survey completion. All surveys can be completed online or by telephone. All health services (e.g., STI testing, condoms) will be provided at no cost to participants in the intervention arm. Charges for any service for participants in the control arm will be billed by the ED provider according to their standard practice.

Visit 1 (screening)	Visit 1 (randomization)	2 mo.	4 mo.	6 mo.
Take computerized screening survey \$5.00	Be randomized into study group and complete assigned arm procedures \$30.00	Take survey online or by phone \$10.00	Take survey online or by phone \$10.00	Take survey online or by phone \$25.00

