5. DATA COLLECTION

Surveys will be administered via REDCap, which enables administration of online surveys via a secure website utilizing a secure sockets layer (SSL) protocol. Electronic data will be stored in an encrypted format on hospital firewall-protected servers, written data will be stored in a locked office. Direct data entry provides a confidential means of survey administration, consistent delivery, and enhanced data accuracy.^{49,50} Data from clinical records will be electronically extracted from hospital databases. Participants will be assigned an anonymous study number. Surveys will be completed confidentially and will not contain identifying information. Contact information will be recorded separately, via a separate REDCap data collection tool, and will be used for notification of test results. This data will include medical record number, date of birth, address, and phone number. We do not plan on collecting social security number as we feel this study will qualify for exemption from Greenphire and have requested exemption. In order to better evaluate the over-all adolescent population in the Main ED we will be collecting refusal data from those potential subjects and their parents who decline to participate.

Secure Storage of Data

Records to be kept and Secure Storage of Data: Survey development, data collection and handling will be conducted through Children's Mercy's REDCap Research software. The Redcap database is protected by Gazzang's zNcrypt product. zNcrypt transparently encrypts and secures data at rest without any changes to your applications or database and ensures there is minimal performance lag in the encryption or decryption process. Advanced key management and process-based access controls enable organizations to meet compliance regulations and ensure unauthorized parties or malicious actors never gain access to the encrypted data. zNcrypt meets compliance for HIPAA, PCI-DSS, FISMA, EU Data Protection, and more.

Data will be exported from REDCap to statistical programs for analysis (i.e. SAS, SPSS, Excel.) All data will be securely stored on password-protected servers. Only personnel involved in the study will have access to the data. Data transfer between members of the study team will be conducted solely within the confines of the CMH network.

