8. HUMAN SUBJECTS

Consent of Participants

We will use our electronic tracking system to identify potential participants to complete the computerized health behavior screening survey.

Consent/assent will be completed in two phases: 1) screening for eligibility and GU complaints with the health survey (see "health screening survey") and 2) formative group/randomized trial.

Subjects aged 14-17 years: For phase 1 (screening), potential subjects and parents will be given study information sheet ("info sheet"). Adolescents will independently provide verbal assent, which mirrors the clinical and legal standard for care. For phase 2, study details will be explained in private and written assent obtained from eligible adolescents who agree to

participate. We will request a waiver of parental permission from the institutional review board (IRB) because adolescents 14 years of age or older can seek reproductive care independently in Missouri and Kansas.

Subjects aged 14-17 years seeking ED care for medically emancipated condition: Since many of this subgroup of patients will likely be unaccompanied by a parent, and since they are able to consent for this type of care independently, we will request a waiver of parental permission for both phases from the IRB. For phase 1, potential subjects will be given study information ("info sheet") and will independently provide verbal assent. For phase 2, the study will be explained in private and written assent obtained from those who agree to participate ("minor written assent").

Subjects aged 18-19 years: For both phases, the study will be explained in private ("info sheet"). Subjects will provide verbal consent for phase 1 and written consent for phase 2 ("adult written consent").

Institutional Review Board (IRB) Review and Informed Consent

This protocol, and any subsequent modifications, will be reviewed and approved by the Pediatric IRB at The Children's Mercy Hospital & Clinics.

Subject Confidentiality

The planned procedures for protecting against or minimizing potential risks are described here.

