APPENDIX 1.

STUDY SCHEMA

FORMATIVE GROUP

PROCEDURE	Part 1 BASELINE Survey	Part 2 INTERVENTION	Part 3 POST-INTERVENTION Survey
Adolescents who meet Part 1 Base-line Inclusion criteria and have no exclusion criteria will be approached and invited to participate in the research study. Research Study Information FORMATIVE GROUP given to parent	X		
Obtain permission to interview teen alone	X		
Obtain verbal consent for FORMATIVE GROUP baseline screening from teen	X		
Teen completes computerized baseline screening survey	X		
Teen meets Part 2 INTERVENTION inclusion criteria	X		
FORMATIVE GROUP Written Consent Obtained		X	
Meets with Health Educator for Part 2 INTERVENTION including Health services offered and		X	
Post-intervention Survey to assess satisfaction with intervention			X

RANDOMIZED CONTROL TRIAL STUDY SCHEMA

PROCEDURE	At Initial ED Visit					
	BASELINE Survey	INTERVENTION	Post INTERVENTION Survey	3 weeks post ED visit	2 and 4 months post ED visit	6 months post ED visit
Adolescents who meet Part 1 Base-line Inclusion criteria and have no exclusion criteria will be approached and invited to participate in the research study. RCT Information given to parent	X					
Obtain permission to interview teen alone	X					
Obtain verbal consent for RCT baseline screening from teen	X					
Teen completes computerized baseline screening survey	X					
Teen meets Part 2 INTERVENTION inclusion criteria	X					
Teen is randomized to either the CONTROL ARM or the INTERVENTION ARM and consented with the appropriate consent form		X				
Meets with Health Educator for Part 2 INTERVENTION		X				
Teen takes post-intervention satisfaction survey			X			
Health Educator fills out post intervention assessment			X			
Medical Chart reviewed for health services utilization by study team				X		
Teen completes brief survey on: sex health behaviors, healthcare utilization, readiness for safer sex					X	X
Assessment of new occurrence of STD or HIV During survey						X

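### Assignments are delivered by numbered sealed envelopes with no stated reason or safeguards, although REDCap generates the sequence and already holds the balancing answer, and the documents disagree on whether consent precedes allocation

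*Combined protocol and SAP*

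**What the plan says.** On the source of the sequence, Section 4 (Recruitment procedures) states: "We will generate our randomization sequence using REDCap, which will also host our computerized surveys". It then says how assignments are made: "Randomization will be assigned based on computer-generated algorithm and using numbered sealed envelopes".

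The same section sets a balancing factor, to be kept 1:1 between arms: "we will ensure balanced allocation of participants reporting genitourinary complaints". It names neither stratification nor blocking. Section 8 gives the screening phase as the point where this factor is captured: "screening for eligibility and GU complaints with the health survey". Section 5 names the platform: "Surveys will be administered via REDCap". Section 4 puts allocation after the survey: "After survey completion, participants will be randomized to receive the intervention or control arm".

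On consent, two places differ. The RCT schema in Appendix 1 reads: "Teen is randomized to either the CONTROL ARM or the INTERVENTION ARM and consented with the appropriate consent form". In Section 3 (Incentives), signing of the written consent comes first, followed by: "If they continue in the study they will be randomized into study group".

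The protocol does not say why envelopes are used, whether they are opaque, who prepares and holds them, in what order they are opened, whether opening is logged, or how the genitourinary groups are kept apart. It does not mention blinding.

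**The concern.** Randomization protects against selection only while nobody who recruits can know or influence the next assignment. Three features make this important here.

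- **The arms cannot be masked.** Controls receive a pamphlet and a resource list. The intervention arm adds a session with the educator. Participants and the educator will know the arm.
- **The outcome can partly be foreseen.** The primary outcome in Section 7 is receipt of any listed service, and intervention participants choose which services, if any, to take. Section 4 justifies its balancing factor by earlier differences in testing according to genitourinary symptoms. That predictor is to be balanced, but other signs of a patient's willingness are not.
- **The plan relies on randomization for this purpose.** Section 7 names it as the protection against self-selection.

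Envelopes depend on physical handling: they can be opened early or out of order unless procedures prevent it, and none is described. If the schema is followed, the arm is also revealed before the adolescent agrees to take part. Agreement could then depend on the arm, and the plan does not say what happens to an assignment whose recipient declines. Section 7 expects the resulting effect size to support a multi-site application, so a bias would carry forward.

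**Working it through.** **1. The plan's own figures.** From Section 7: planned rates .15 and .50, alpha .05, 38 per arm, power .94.

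- Planned difference: .50 − .15 = .35.
- Unpooled normal approximation: SE = √[(.15 × .85 + .50 × .50)/38] = √(.3775/38) = .0997. Then .35/.0997 − 1.96 = 1.55, and Φ(1.55) = .94. This reproduces the stated power. The pooled form gives .92.
- With 25% loss from 40 per arm (30 per arm), the pooled form gives .843 two-sided and .911 one-sided, matching the stated .84 and .91.

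How assignments are released changes none of these. The issue is bias, not power.

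**2. Is the balancing answer in REDCap when allocation happens?** Genitourinary complaints are recorded in the screening survey (Section 8). Surveys run in REDCap (Section 5). Randomization follows the survey (Section 4). So when the arm is assigned, REDCap has produced the sequence and holds the answer needed to balance it. The envelopes move the final step outside that system.

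**3. Order of consent and allocation.**

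| Place | Order |
|---|---|
| Section 3, Incentives | written consent signed, then randomized |
| Appendix 1, RCT schema | randomized, then consented with the form that fits the arm |

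Both cannot hold. Under the second, the arm is known before consent whichever tool releases it.

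**4. Illustrative size of a bias (assumptions, not in the documents).** Suppose k likely acceptors due for control are exchanged with k unlikely acceptors due for the intervention. Let g_I and g_C be the gap in uptake probability between the two kinds of patient under each arm. With 40 per arm:

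shift in difference = (k/40) × (g_I + g_C)

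With g_I = .50 assumed:

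| k | g_C = .15 | g_C = .30 | g_C = .50 |
|---|---|---|---|
| 2 | .0325 | .04 | .05 |
| 4 | .065 | .08 | .10 |
| 6 | .0975 | .12 | .15 |

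For k = 4: (4/40) × (.50 + .15) = .065, and (4/40) × (.50 + .50) = .10. Against the planned .35 these are 19% and 29%.

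The right-hand column is an upper case. If a share q of patients are likely acceptors and the control mean is .15, then (uptake in the others) + .50q = .15. Uptake cannot be negative, so q is at most .15/.50 = .30.

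**The case against.** The strongest reply is that numbered sealed envelopes are an accepted concealment method when they are opaque, opened in order and held independently, so this is a preference plus some missing detail. The first half stands: using envelopes is not an error. But none of those conditions is stated, and the better alternative would use a system already in the trial.

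The plan also has partial protections. Patients are approached in sequence by arrival and availability, and recruitment shifts follow the previous year's arrivals (Section 4). Refusal data are collected (Section 5). Baseline characteristics are compared between arms (Section 7). These limit discretion or may reveal steering afterwards. They do not conceal the next assignment.

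Several stronger readings are tempting but not supported:

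- **That the envelopes bring no benefit.** The protocol gives no reason for them, but silence does not show that there is none. Use in waiting rooms or treatment spaces is a possible practical one.
- **That release depends on envelopes alone.** The sentence names an algorithm and envelopes together and leaves their relation unclear.
- **That staff in the ED keep two series and choose between them by hand.** No location, custodian or mechanism is described. Balancing by envelope would need separate sets or some other step, but the plan specifies neither.
- **That recruiters have a motive to steer.** Nothing in the documents shows this.
- **That a bias of .10 should be expected.** It needs four swaps and a .50 gap in both arms, which is hard to square with a planned control rate of .15.

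Finally, the documents do not say that real-time release in REDCap is available to this study. The recommendation assumes it is.

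**Conclusion.** The point holds as an avoidable weakness that should be corrected, not as a demonstrated error or evidence of bias. The documents establish that REDCap generates the sequence and holds the balancing answer before allocation, that delivery nonetheless involves envelopes with no reason or safeguards stated, and that the trial is open-label in effect. That envelopes are easier to subvert than an electronic release is a methodological judgement.

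The best-supported part is the conflict over consent. If the Appendix 1 order is followed, allocation is not concealed at the moment of consent, and no change of release tool would cure that.

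No size can be derived from the documents. The shift of about .065 to .10 for four swapped pairs rests on an assumed number of swaps, an assumed gap of .50 in the intervention arm and an assumed gap of .15 to .50 in the control arm.

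**What to change.** - **Section 4.** Replace the envelope sentence. REDCap releases each assignment in real time, stratified by the genitourinary answer in the screening survey, only after written consent (or assent) is recorded. Each release is time-stamped and logged, and recruiters have no access to the allocation table.
- **Backup.** Keep opaque, sequentially numbered envelopes, in separate sets by genitourinary group, for system downtime only, with every opening logged. If real-time release is not available to this study, say why envelopes are used and specify opacity, sets by genitourinary group, independent custody, strict order and an opening log.
- **Section 3 and Appendix 1.** Reconcile the two passages so that written consent precedes allocation in both.

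The cost is a short REDCap set-up, the protocol edits and, if the consent forms are arm-specific as the schema suggests, possible revision of those forms with IRB review. Sample size, alpha and power do not change.

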5. DATA COLLECTION

Surveys will be administered via REDCap, which enables administration of online surveys via a secure website utilizing a secure sockets layer (SSL) protocol. Electronic data will be stored in an encrypted format on hospital firewall-protected servers, written data will be stored in a locked office. Direct data entry provides a confidential means of survey administration, consistent delivery, and enhanced data accuracy.^{49,50} Data from clinical records will be electronically extracted from hospital databases. Participants will be assigned an anonymous study number. Surveys will be completed confidentially and will not contain identifying information. Contact information will be recorded separately, via a separate REDCap data collection tool, and will be used for notification of test results. This data will include medical record number, date of birth, address, and phone number. We do not plan on collecting social security number as we feel this study will qualify for exemption from Greenphire and have requested exemption. In order to better evaluate the over-all adolescent population in the Main ED we will be collecting refusal data from those potential subjects and their parents who decline to participate.

Secure Storage of Data

Records to be kept and Secure Storage of Data: Survey development, data collection and handling will be conducted through Children's Mercy's REDCap Research software. The Redcap database is protected by Gazzang's zNcrypt product. zNcrypt transparently encrypts and secures data at rest without any changes to your applications or database and ensures there is minimal performance lag in the encryption or decryption process. Advanced key management and process-based access controls enable organizations to meet compliance regulations and ensure unauthorized parties or malicious actors never gain access to the encrypted data. zNcrypt meets compliance for HIPAA, PCI-DSS, FISMA, EU Data Protection, and more.

Data will be exported from REDCap to statistical programs for analysis (i.e. SAS, SPSS, Excel.) All data will be securely stored on password-protected servers. Only personnel involved in the study will have access to the data. Data transfer between members of the study team will be conducted solely within the confines of the CMH network.

6. STUDY DURATION/STUDY TIMELINE

We expect to consent 500 subjects into this study in order to obtain 6 completed subjects in the Formative phase and 80 completed subjects into the RCT phase of this study.

Formative Participant Involvement (n=6):

Timeline of assessments			
	At initial ED visit		
	Part 1	Part 2	Part 3
	Baseline	Intervention	Post Intervention
Demographics	X		
Sexual health behaviors	X		
Theory Planned Behavior (TPB) measures (e.g., attitudes, risk perception, intentions)	X	X	
Health services offered, accepted		X	
Healthcare utilization*	X		
Satisfaction measures			X
Fidelity to motivational interviewing**			X
Readiness for safer sex/service uptake	X		
Current or incident HIV or STI #	X		

*Assessed via self-report and hospital medical record; **Intervention participants only;
Assessed via study testing, self-report, and/or hospital medical record

RCT Participant Involvement (n=80):

Timeline of assessments	Part 1		Part 2			
	At initial ED visit		Time from initial visit			
	Baseline	Post-treatment	3 wk	2 mo	4 mo	6 mo
Demographics	X					
Sexual health behaviors	X			X	X	X
Theory Planned Behavior (TPB) measures (e.g., attitudes, risk perception, intentions)	X	X				X
Health services offered, accepted		X				
Healthcare utilization*	X		X	X	X	X
Satisfaction measures		X				
Fidelity to motivational interviewing**		X				
Readiness for safer sex/service uptake	X	X		X	X	X
Current or incident HIV or STI #	X					X

*Assessed via self-report and hospital medical record; **Intervention participants only; # Assessed via study testing, self-report, and/or hospital medical record

